#### 6.2 Definitions

## 6.2.1 Definition of Adverse Event

An adverse event (AE) is any untoward medical occurrence in a patient receiving study treatment and which does not necessarily have a causal relationship with this treatment. An AE can therefore be any unfavorable and unintended sign (including an abnormal laboratory finding), symptom, or disease temporally associated with the use of an experimental intervention, whether or not related to the intervention.

#### 6.2.2 Severity of Adverse Events

The severity of an AE is graded as follows:

Mild (grade 1): the event causes discomfort without disruption of normal daily activities.

Moderate (grade 2): the event causes discomfort that affects normal daily activities.

Severe (grade 3): the event makes the patient unable to perform normal daily activities or significantly affects his/her clinical status.

Life-threatening (grade 4): the patient was at risk of death at the time of the event.

Fatal (grade 5): the event caused death.

#### 6.2.3 Serious Adverse Events

A "serious" adverse event is defined in regulatory terminology as any untoward medical occurrence that:

Results in death.

If death results from (progression of) the disease, the disease should be reported as event (SAE) itself.

Is life-threatening (i.e. the patient was at risk of death at the time of the event).

Requires in-patient hospitalization or prolongation of existing hospitalization for ≥ 24 hours.

Results in persistent or significant disability or incapacity.

Is an important medical event. Essentially, any event that does not meet the above criteria, but that in the judgment of the investigator jeopardizes the patient, may be considered for reporting as a serious adverse event.

For the purposes of this study, the adverse events that would meet any of these criteria are: maternal death, ICU admission, anaphylaxis, hysterectomy will be documented and reported as a SAE. In addition, any unexpected event which the PI believes to have been cause or contributed to by the intervention, regardless of whether it resulted in hospitalization, will also be considered an AE or SAE.

#### 6.3 Steps to Determine If an Adverse Event Requires Expedited Reporting

Step 1: Identify the type of adverse event

Step 2: Grade the adverse event

Step 3: Determine whether the adverse event is related to the protocol therapy

Attribution categories are as follows:

- Definite The AE is clearly related to the study treatment.
- Probable The AE is likely related to the study treatment.
- Possible The AE *may be related* to the study treatment.

- Unrelated - The AE is clearly NOT related to the study treatment.

## Step 4: Determine the prior experience of the adverse event.

Expected events are those that have been previously identified as resulting from administration of the agent. An adverse event is considered unexpected, for expedited reporting purposes only, when either the type of event or the severity of the event is not listed in:

- the current known adverse events listed in the Agent Information Section of this protocol:
- the drug package insert;
- the current Investigator's Brochure

## 6.4 Reporting Requirements for Adverse Events

## 6.4.1 Expedited Reporting

- The Principal Investigator will be notified within 24 hours of learning of any serious adverse events, regardless of attribution, occurring during the study or within 30 days of the last administration of the study drug.
- The University of Pennsylvania IRB must be notified within 10 business days of "any unanticipated problems involving risk to subjects or others" (UPR/UPIRSO).

The following events meet the definition of UPR:

- Any serious event (injuries, side effects, deaths or other problems), which in the opinion of the Principal Investigator was unanticipated, involved risk to subjects or others, and was possibly related to the research procedures.
- 2. Any serious accidental or unintentional change to the IRB-approved protocol that alters the level of risk.
- 3. Any deviation from the protocol taken without prior IRB review to eliminate apparent immediate hazard to a research subject.
- 4. Any new information (e.g., publication, safety monitoring report, updated sponsor safety report), interim result or other finding that indicates an unexpected change to the risk/benefit ratio for the research.
- 5. Any breach in confidentiality that may involve risk to the subject or others.
- 6. Any complaint of a subject that indicates an unanticipated risk or that cannot be resolved by the Principal Investigator.

## 6.4.2 Routine Reporting

All other adverse events- such as those that are expected, or are unlikely or definitely not related to the study participation- are to be reported annually as part of regular data submission.

## 6.5 Stopping Rules

This study does not have a primary safety endpoint or place study subjects at high risk.

## 7 STUDY DESIGN/STUDY ENDPOINTS

This will be a prospective, randomized, single center study on the efficacy of Pitocin(oxytocin) versus oral misoprostol for PROM induction in nulliparous women with unfavorable cervical examinations. Please refer to section 2.3 for endpoints.

## 7.1 Sample Size and Accrual

The sample size is based on the mean time to delivery with Pitocin(oxytocin) after PROM IOL of 10.4 hours, with a standard deviation of 4.3 hours. For a power of 80% and an alpha of 0.05, 148 women would be needed to find a 2-hour difference in time to delivery. To account for drop out, we plan to enroll 155 women.

We estimate 15-20 eligible women deliver at HUP per month. We anticipate approaching 80% of these women or approximately 14 per month. With an estimated 50% consent rate, we would enroll approximately 7 women per month. Therefore, we would need 24 months to reach our target enrollment of 155 women.

## 7.2 Data Analyses Plans

Measures of relative risk will include 95% confidence intervals. Descriptive statistics will be presented as mean with standard deviation, median with interquartile range, or proportion with 95% confidence interval based on data type and distribution. Comparisons between groups will be performed using a Chi-square or Fisher's exact test for categorical variables and parametric or non-parametric tests for continuous variables, as appropriate. Intention-to-treat analyses will be conducted such that all patients with available follow-up measures will be included in the analysis. Statistical analyses were conducted in STATA, version 12.0 (College Station, Texas). Two-tailed P values of <0.05 will be considered statistically significant.

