# **Study Summary**

Title	Pitocin or Oral Misoprostol for PROM IOL in
	Nulliparous Women with Unfavorable Cervical
	Exams
Short Title	POM PROM
Methodology	Randomized trial
Study duration	24 Months
Study Center (s)	Single-center
Objective	To determine if Pitocin (oxytocin) or oral
	misoprostol results in a shorter interval to
	delivery after the start of induction in nulliparous
	women with unfavorable cervical exams with
	premature rupture of membranes (PROM).
Number of Subjects	155
Diagnosis and Main Inclusion Criteria	PROM ≥ 36 weeks gestation; Singleton gestation
	in vertex presentation; Cervix ≤ 2 cm dilated and
	Bishop < 8; No contraindication to vaginal
	delivery; No evidence of infection
Study Product (s), Dose, Route, Regimen	Oral Misoprostol – 50 mcg q4H
	IV Pitocin (Oxytocin) – 2 mU/min, increased by 2
	mU/min to achieve 4-5 contractions in 10
	minutes with cervical change. Max dose 40
	mU/min
Duration of administration	Oral Misoprostol – Max 6 doses or until cervical
	ripening and/or delivery has been achieved
	Pitocin – Until delivery
Primary Outcome	Time from IOL to delivery (hours)
Statistical methodology	Intention to treat analysis, chi-square test for
	categorical variables, two-sample t-test for
	continuous variables

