#### 3.1 Inclusion Criteria

**English-speaking** 

≥ 18 years of age

PROM ≤24 hours with no evidence of labor

PROM - Standard clinical diagnosis

Labor – >3 painful contractions in a 10 minute period, averaged over 30 minutes

≥ 36 weeks gestation

Agreeable to induction of labor

Singleton pregnancy

Vertex presentation

Cervical dilation ≤ 2 cm and Bishop score < 8

Exam done by senior resident, fellow, midwife or attending to confirm eligibility

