#### 8.2 Collection of data

We will record data on each patient regarding their demographics, obstetrical and medical history, labor and delivery admission through postpartum discharge. We will also collect neonatal outcomes on their infants through hospital discharge.

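### Cheap improvement: adjust the primary comparison of time to delivery for the eligibility Bishop score, in one named mean-difference analysis with a 95% CI

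*Combined protocol and SAP*

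**What the plan says.** - **Test.** For continuous variables the Study Summary gives a t-test ("categorical variables, two-sample t-test for" continuous variables). Section 7.2 permits "parametric or non-parametric tests for continuous variables, as appropriate", with no criterion for choosing and no separate statement for the primary endpoint. Neither place mentions a covariate.
- **Intervals.** Section 7.2 says "Measures of relative risk will include 95% confidence intervals" and also gives intervals for proportions. It mentions none for a difference in hours. Continuous data may be summarised either way: "Descriptive statistics will be presented as mean with standard deviation, median with interquartile range".
- **Analysis set.** Section 7.2 says "all patients with available follow-up measures will be included in the analysis".
- **Sizing.** Section 7.1 assumes a mean of 10.4 h and an SD of 4.3 h, and states that "148 women would be needed to find a 2-hour difference in time to delivery" at 80% power and alpha 0.05. The plan is to enrol 155.
- **Baseline score.** Section 3.1 requires "Cervical dilation ≤ 2 cm and Bishop score < 8", confirmed by an exam. Section 8.2 lists the data to be recorded in general terms ("obstetrical and medical history, labor and delivery admission through postpartum discharge") and does not name the Bishop score.

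**The concern.** The Bishop score is assessed before randomisation, and it is a natural candidate predictor of how long an induction takes. If it does predict duration, an unadjusted comparison leaves explainable variation in the error term. The confidence interval is then wider, and power lower, than the same women could give. Regression on arm and the score targets the same mean difference in hours that section 7.1 is sized on, without one extra participant.

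The place to make this change is the sentence that leaves the test open. The Summary and section 7.2 are compatible but not identical, and neither plans an interval for the difference in hours. If medians and interquartile ranges alone were reported, a reader could not rebuild that interval. A single named primary analysis settles this along with the adjustment.

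**Working it through.** **Inputs.** SD 4.3 h, difference 2 h, 148 women and alpha 0.05 (section 7.1); two-sided testing (section 7.2). Assumptions: 1:1 allocation (not stated) and the same SD in both arms.

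**1. The plan's own figure.** A two-sided two-sample t-test needs 73.5, so 74 women per arm, 148 in total. This matches section 7.1; the normal approximation gives 146. The standard error is 4.3 × √(2/74) = 0.707 h and the noncentrality is 2/0.707 = 2.83. On 146 degrees of freedom power is 80.2%. The sample size therefore rests on an unadjusted mean difference.

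**2. Precision of that analysis.** The expected 95% CI half-width is 1.976 × 0.707 = 1.40 h at 148 women, and 1.36 h at 155.

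**3. Adjustment for the Bishop score.** Let R² be the share of variance in duration explained by the score. The residual SD is 4.3 × √(1 − R²). One covariate costs one degree of freedom (145 remain) and multiplies the variance by about 1 + 1/144. So SE = 4.3 × √(1 − R²) × √(2/74) × √(1 + 1/144).

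| Assumed R² | Residual SD (h) | SE (h) | CI half-width (h) | Power for 2 h |
|---|---|---|---|---|
| unadjusted | 4.30 | 0.707 | 1.40 | 80.2% |
| 0% | 4.30 | 0.709 | 1.40 | 80.0% |
| 4% | 4.21 | 0.695 | 1.37 | 81.6% |
| 10% | 4.08 | 0.673 | 1.33 | 83.9% |
| 20% | 3.85 | 0.634 | 1.25 | 87.9% |

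Leaving aside the lost degree of freedom, adjustment breaks even when (1 − R²)(1 + 1/144) = 1, that is at R² = 1/145, about 0.7%.

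**4. Check by simulation.** 20,000 trials per cell were run with gamma errors and scores uniform on 0-7, both assumptions. At R² = 0 power was 80.1% for the t-test, 79.9% for regression with HC1 standard errors and 79.3% with HC3. Type I error with HC1 was 4.7-5.2% over all R² values tried.

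**5. Missing scores.** With 10% of scores missing at random (assumption) and HC1, power was:

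| R² | Overall-mean imputation | Complete cases only |
|---|---|---|
| 0% | 79.9% | 75.6% |
| 10% | 83.5% | 79.8% |
| 20% | 87.0% | 84.0% |

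The missing-data rule matters more than the cost of the covariate.

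**6. Mean-based against rank-based test.** 40,000 trials per cell were run at 74 per arm, with mean 10.4 and SD 4.3. The shapes are assumptions.

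| Effect | Test | Normal | Gamma | Lognormal |
|---|---|---|---|---|
| None | t | 4.9% | 4.9% | 5.0% |
| None | rank | 4.8% | 4.8% | 5.0% |
| 2-hour shift | t | 80.1% | 80.1% | 80.1% |
| 2-hour shift | rank | 78.2% | 83.0% | 88.7% |
| Proportional (10.4 to 8.4 h) | t | 87.2% | 87.8% | 87.8% |
| Proportional (10.4 to 8.4 h) | rank | 85.3% | 84.7% | 88.7% |

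**The case against.** **The gain is speculative.** No correlation between Bishop score and duration is given, and eligibility restricts the score to below 8 with dilation of at most 2 cm, which may leave it little predictive spread. This stands. The table shows a range, not a forecast, and leaving out adjustment is not a defect.

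**A mean-based analysis can lose power.** Under a pure 2-hour shift with skewed times, the rank test reached 83-89% against about 80%. This also stands, although under a proportional effect the order is mixed. The loss is accepted because section 7.1 sizes the trial on a difference in means.

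**The test is already named.** The Summary gives the t-test and section 7.2 permits it. If mean and SD are reported, the interval can be rebuilt. So naming the test and adding the interval amount to clarification.

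**A stronger reading that the documents do not support.** A reader might infer that the open choice of test makes the primary analysis invalid. In the simulations the two tests disagreed on significance in roughly 4-10% of trials with a true effect. That is a difference between two valid tests, not an error rate: each keeps type I error at 4.8-5.0%. Choosing by a normality pre-test gave type I error of 5.4-5.8% in one simulation and 4.7-5.0% in a larger one. Only reporting whichever P value is smaller reached about 6.2-6.6%, and nothing in the documents proposes that.

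**Conclusion.** The point holds as a low-cost improvement. The primary endpoint is to be compared without adjustment although a pre-randomisation score is assessed for every woman. At 148 women, adjustment would change power for 2 h from 80.2% to about 80.0, 81.6, 83.9 or 87.9% at R² of 0, 4, 10 or 20%. The downside is a fraction of a point and the upside is up to about 8 points at the top of the assumed range. Its real size is unknown from the documents and may be small. The figures rest on 1:1 allocation, the SD in section 7.1 and an assumed R². The plan as written is not invalid.

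**What to change.** In both the Study Summary and section 7.2, name one primary analysis:

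- **Estimate.** The mean difference in hours from start of induction to delivery, with 95% CI and P value, from linear regression on arm and the eligibility Bishop score, with HC1 standard errors.
- **Missing scores.** Replace a missing score by the overall baseline mean, so that all women with follow-up stay in the analysis, as section 7.2 intends.
- **Sensitivity analyses.** The unadjusted t-test with its 95% CI, stating the variance assumption (148 reproduces with pooled variance), and the Wilcoxon test.

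**Cost.** No extra women or visits, and no change to 148 or 155. The numeric score must be entered in REDCap, because section 8.2 does not name it. Power falls by about 0.2-0.3 points if the score is unrelated to duration. A mean-based primary analysis may also have less power than a rank test if times are strongly skewed and the effect is a pure shift.

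If the team prefers not to adjust, naming the t-test in both places and adding its 95% CI still reconciles the two sections. That is wording only and brings no gain in precision.

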#### 8 STUDY MANAGEMENT

#### 8.1 Conflict of Interest

Any investigator who has a conflict of interest with this study (patent ownership, royalties, or financial gain greater than the minimum allowable by their institution, etc.) must have the conflict reviewed by the PI and the IRB. All investigators will follow the University's conflict of interest policy.

#### 8.2 Collection of data

We will record data on each patient regarding their demographics, obstetrical and medical history, labor and delivery admission through postpartum discharge. We will also collect neonatal outcomes on their infants through hospital discharge.

## 8.2.1 Private information

Only the study staff listed on the protocol approved by the Institutional Review Board will have access to individually identifiable private information about human subjects. The only individually identifiable private information about human subjects that will be collected for research purposes is the subject's name and medical record number for the purpose of linking the subject to their unique study identifier.

## 8.2.2 Data Protection

The individually identifiable private information that will be collected is name and medical record number for the purposes on linking the subject to their unique study number for chart review. The file linking the study number to the name, medical record number and phone number will be kept in a password-protected file on a secure server. Data will be

collected primarily by the research team. The electronic database (REDCap) will be stored behind the institution's firewall in a password-protected file.

## 8.3 Institutional Review Board (IRB) Approval and Consent

It is expected that the IRB will have the proper representation and function in accordance with federally mandated regulations. The IRB should approve the consent form and protocol.

In obtaining and documenting informed consent, the investigator should comply with the applicable regulatory requirement(s), and should adhere to Good Clinical Practice (GCP) and to ethical principles that have their origin in the Declaration of Helsinki.

Before recruitment and enrollment onto this study, the patient will be given a full explanation of the study and will be given the opportunity to review the consent form. Each consent form must include all the relevant elements currently required by the FDA Regulations and local or state regulations. Once this essential information has been provided to the patient and the investigator is assured that the patient understands the implications of participating in the study, the patient will be asked to give consent to participate in the study by signing an IRB-approved consent form.

Prior to a patient's participation in the trial, the written informed consent form should be signed and personally dated by the patient and by the person who conducted the informed consent discussion.

## 8.4 Data Management and Monitoring/Auditing

#### 8.4.1 Data Safety and Monitoring Plan

Safety monitoring will be performed periodically by the principal investigator. This will include assessment of accuracy of data recording, assuring de-identification of data, and that there is appropriate locked storage of data material. There will be no planned interim analyses. An advisory board will be created for continual oversight of the project. It will be comprised of faculty members within the department with extensive experience in prospective clinical trials. They will perform periodic reviews of safety data from this study. The DSMB that will be created is attached.

#### 8.5 Adherence to the Protocol

Except for an emergency situation in which proper care for the protection, safety, and well-being of the study patient requires alternative treatment, the study shall be conducted exactly as described in the approved protocol.

## 8.5.1 Emergency Modifications

Investigators may implement a deviation from, or a change of, the protocol to eliminate an immediate hazard(s) to trial subjects without prior IRB approval.

For any such emergency modification implemented, a IRB modification form must be completed within five (5) business days of making the change.

#### 8.5.2 Other Protocol Deviations/Violations

All other planned deviations from the protocol must have prior approval by the Principal Investigator and the IRB. According to the IRB, a protocol deviation is any unplanned variance from an IRB approved protocol that:

- Is generally noted or recognized after it occurs
- Has no substantive effect on the risks to research participants
- Has no substantive effect on the scientific integrity of the research plan or the value of the data collected
- Did not result from willful or knowing misconduct on the part of the investigator(s).

An unplanned protocol variance is considered a violation if the variance:

- Has harmed or increased the risk of harm to one or more research participants.
- Has damaged the scientific integrity of the data collected for the study.
- Results from willful or knowing misconduct on the part of the investigator(s).
- Demonstrates serious or continuing noncompliance with federal regulations, State laws, or University policies.

If a deviation or violation occurs without prior approval from the Principal Investigator, the ensuing guidelines will be followed:

**Protocol Deviations:** Personnel will report to any sponsor or data and safety monitoring committee in accordance with their policies. Deviations should be summarized and reported to the IRB at the time of continuing review.

**Protocol Violations:** Study personnel should report violations within one (1) week of the investigator becoming aware of the event using the same IRB online mechanism used to report Unanticipated Problems.

#### 8.6 Record Retention

Study documentation includes all Case Report Forms, data correction forms or queries, source documents, monitoring logs/letters, and regulatory documents (e.g., protocol and amendments, IRB correspondence and approval, signed patient consent forms).

Source documents include all recordings of observations or notations of clinical activities and all reports and records necessary for the evaluation and reconstruction of the clinical research study.

Government agency regulations and directives require that the study investigator must retain all study documentation pertaining to the conduct of a clinical trial. In all other cases, study documents should be kept on file until three years after the completion and final study report of this investigational study.

#### 8.7 Obligations of Investigators

The Principal Investigator is responsible for the conduct of the clinical trial at the site in accordance with Title 21 of the Code of Federal Regulations and/or the Declaration of Helsinki. The Principal Investigator is responsible for personally overseeing the treatment of all study patients. The Principal Investigator must assure that all study site personnel, including sub-investigators and other study staff members, adhere to the study protocol and all FDA/GCP/NCI regulations and guidelines regarding clinical trials both during and after study completion.

The Principal Investigator will be responsible for assuring that all the required data will be collected and entered onto the Case Report Forms. Periodically, monitoring visits will be conducted and the Principal Investigator will provide access to his/her original records to permit verification of proper entry of data. At the completion of the study, all case report forms will be reviewed by the Principal Investigator and will require his/her final signature to verify the accuracy of the data.

